3. Non-English speaking patients
4. Scheduled for or with a history of pancreatic surgery (e.g. TPIAT, Puestow, Frey, Whipple, other)
5. Currently undergoing or about to start endoscopic therapy with ERCP or EUS
6. Recent history of acute pancreatitis as defined by the Revised Atlanta Classification within a month prior to enrollment
7. Radiologic and clinical findings consistent with symptomatic pseudocyst, wall-off necrosis, infected pancreatic necrosis, or biliary obstruction within the last 6 months
8. Self-reported daily use of opioids for > 12 months for weak opioids (codeine, tramadol and hydrocodone) or > 6 months for strong opioids (other opioids) in the last two years. A similar approach was used in a recent landmark RCT that compared endoscopic therapy vs. surgery in patients with painful chronic pancreatitis.¹⁹
9. Self-reported ongoing illicit drug use or abuse
10. Suspected or diagnosed pancreatic cancer
11. Receiving chemotherapy for cancer
12. Known allergy to adhesive ECG electrodes
13. Patients with bilateral below the knee amputation
14. Patients with lower extremity paralysis
15. Patients are participating in another clinical trial
16. Patients with an implantable electrical stimulation device.

Interventions

I. Run-in period: 2 weeks (V0)

After initial screening (V0 – virtual or in person) and after the consent form is signed, subjects that fulfill eligibility criteria will be invited to participate to the study.

All eligible subjects will then complete a pre-enrollment run-in period of 2 weeks. Over this run-in period, subjects will be asked to complete a diary with information on daily severity of abdominal pain. Subjects will rate their worst daily abdominal pain intensity over the past 24 hours by putting a mark on a visual analogue scale (scoring 0-10), where 0 represents “no pain” and 10 represents the “worst imaginable pain.” Subjects with abdominal pain severity of 4 or greater for at least 5 days in this run-in period will be invited for a site visit to start the intervention (V1). Subjects who don’t qualify for this criterion will not be invited to receive the intervention. A similar approach has been used in a prior RCT evaluating the role of antioxidants for pain in CP.²⁰ Surveys will be completed via RedCap.

II. Visit 1 (V1)

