3. Comprehensive Pain Assessment Tool Short Form for Chronic Pancreatitis (COMPAT-SF) [timeframe - baseline, 4 weeks from treatment onset, 8 weeks from treatment onset]: The COMPAT-SF is a validated self-reported tool specifically designed for patients with pancreatic disease. The COMPAT-SF carries several sub-scores for pain pattern, pain severity, pain provocation, pain spreading, and pain description. The pain pattern scale ranges from 50-100 with higher scores denoting worse pain. The severity score ranges from 0-100 with higher scores denoting worse pain. The provocation score ranges from 0-70 with higher scores denoting worse pain. The spreading score ranges from 0-90 with higher scores denoting worse pain. The description score ranges from 0-80 with higher scores denoting worse pain. The total score ranges from 15-90 with higher scores denoting worse pain.
4. Number of patients using prescription opioids for pain control at time of assessment [timeframe - baseline, 4 weeks from treatment onset, 8 weeks from treatment onset]: Opioid use (yes/no binary answer) at each assessment.

5. Mean reported daily opioid dose for patients using prescription opioids at time of assessment [timeframe - baseline, 4 weeks from treatment onset, 8 weeks from treatment onset]: Opioid dose (continuous variable in milligrams of morphine equivalent) at each assessment.
6. Overall Quality of Life [timeframe - baseline, 4 weeks from treatment onset, 8 weeks from treatment onset]: Overall quality of life will be assessed using the PROMIS-29 instrument. The PROMIS-29 instrument incorporates 7 domains: physical functioning, fatigue, pain interference, depression, anxiety, ability to participate in social roles and activities, and sleep disturbance. Each of these domains have a score 0-40 with higher scores representing worse quality of life in these domains. There are also 2 summary scores: Physical Health and Mental Health. Z-scores are calculated for these two summary scores with lower scores representing better quality of life.
7. Change from baseline on the Hospital Anxiety and Depression Scale (HADS) [timeframe - baseline, 4 weeks from treatment onset, 8 weeks from treatment onset]: The HADS is a validated self-reported tool that screens for symptoms of anxiety and depression. Possible scores range from 0 to 21 (higher scores reflect more severe symptoms of anxiety or depression).

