All data will then be captured in a password-protected database through Redcap. Several methods will be used to promote data quality and integrity including database development, proper training of study team members, and use of data quality rules and validation. Each subject will be assigned a unique random number, and Protected Health Information will be coded to

ensure no one outside the study team will be able to identify a subject's identity. This database will be stored in a password-protected database, in a password-protected folder on a secure server behind the University of Michigan firewall. The information will, at all times, only be able to be accessed by the study investigators.

F. After enrollment is completed, study subjects who enrolled and received TEA will be reached out via a phone call to assess on global impression and acceptability of the treatment. Study subjects will be asked the following questions in relation to the use of TEA on their chronic pancreatitis pain.

- Patient global impression of change (PGIC): this is a 1-item question that should take less than 1 minute
- Modified abbreviated acceptability rating profile: this is an 8-item questionnaire that should take 2 minutes (Tarnowski KJ, Simonian SJ. Assessing treatment acceptance: the Abbreviated Acceptability Rating Profile. *J Behav Ther Exp Psychiatry* 1992;23:101-6).
- Two open questions: (i)“How did the TEA device help you in managing your pancreatitis pain?” and (ii)“What modifications would you suggest to improve the TEA treatment?”

5. Statistical methods

Sample size calculation

We will conduct an open-label pilot study of 10 subjects with CP that fulfill eligibility criteria and that receive the TEA device during visit 1. This will serve to inform feasibility on enrollment, adherence, retention, and completion of data collection. Data obtained in this study will lead to protocol changes for a larger randomized controlled trial that we will plan in the future. The study will be under powered to address any clinical outcomes. We anticipate attrition of approximately 10% for a study of this nature.

Statistical analysis

All analyses will be performed according to the intention-to-treat principle. All primary outcomes will be measured using descriptive statistics as absolute values (percentage), mean \pm standard deviation (SD), and median (interquartile range [IQR]), as appropriate.

Primary outcomes

A. Enrollment feasibility:

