- Rank-sum test or paired t test depending on data distribution to compare pain severity after completion of treatment compared to pain severity from the last week of treatment.
- Pain by COMPAT-SF
 - Mean \pm SD of COMPAT-SF score at onset of treatment (at baseline during visit 1)
 - Mean \pm SD of COMPAT-SF score at end of treatment (at 4 weeks during visit 2)
 - Mean \pm SD of COMPAT-SF score at end of follow-up without treatment (at 8 weeks)
 - Mean difference of COMPAT-SF score from end of treatment compared to score at baseline.
 - Rank-sum test or paired t test depending on data distribution to compare COMPAT-SF score from end of treatment compared to baseline score

- Mean difference of COMPAT-SF score at end of follow-up without treatment compared to score at baseline
- Rank-sum test or paired t test depending on data distribution to compare COMPAT-SF score from end of follow-up without treatment compared to baseline score
- Mean difference of COMPAT-SF score at end of follow-up without treatment compared to score at end of treatment
- Rank-sum test or paired t test depending on data distribution to compare COMPAT-SF score from end of follow-up without treatment compared to score at end of treatment
- Proportion of patients using opioids
 - Proportion of patients using prescription opioids for pain control at onset of treatment (at baseline during visit 1)
 - Proportion of patients using prescription opioids for pain control at end of treatment (at 4 weeks during visit 2)
 - Proportion of patients using prescription opioids for pain control at end of follow-up without treatment (at 8 weeks)
 - McNemar Test to compare proportion of patients using opiates at end of treatment compared to baseline
 - McNemar Test to compare proportion of patients using opiates at end of follow-up without treatment compared to baseline
 - McNemar Test to compare proportion of patients using opiates at end of follow-up without treatment compared to end of treatment
- Reported dose of opiates by milligrams of morphine equivalent (MME)
 - Mean \pm SD of MME at onset of treatment (at baseline during visit 1)
 - Mean \pm SD of MME at end of treatment (at 4 weeks during visit 2)
 - Mean \pm SD of MME at end of follow-up without treatment (at 8 weeks)
 - Mean difference of MME from end of treatment compared to baseline.
 - Rank-sum test or paired t test depending on data distribution to compare MME from end of treatment compared to baseline

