 - Mean difference of MME at end of follow-up without treatment compared to baseline
 - Rank-sum test or paired t test depending on data distribution to compare MME from end of follow-up without treatment compared to baseline
 - Mean difference of MME at end of follow-up without treatment compared to MME at end of treatment
 - Rank-sum test or paired t test depending on data distribution to compare MME from end of follow-up without treatment compared to MME at end of treatment
- Physical quality of life (QOL)
 - Mean \pm SD of physical QOL at onset of treatment (at baseline during visit 1)
 - Mean \pm SD of physical QOL at end of treatment (at 4 weeks during visit 2)
 - Mean \pm SD of physical QOL at end of follow-up without treatment (at 8 weeks)
 - Mean difference of physical QOL from end of treatment compared to baseline.
 - Rank-sum test or paired t test depending on data distribution to compare physical QOL from end of treatment compared to baseline

- Mean difference of physical QOL at end of follow-up without treatment compared to baseline
- Rank-sum test or paired t test depending on data distribution to compare physical QOL from end of follow-up without treatment compared to baseline
- Mean difference of physical QOL at end of follow-up without treatment compared to physical QOL at end of treatment
- Rank-sum test or paired t test depending on data distribution to compare physical QOL from end of follow-up without treatment compared to physical QOL at end of treatment
- Mental quality of life (QOL)
 - Mean \pm SD of mental QOL at onset of treatment (at baseline during visit 1)
 - Mean \pm SD of mental QOL at end of treatment (at 4 weeks during visit 2)
 - Mean \pm SD of mental QOL at end of follow-up without treatment (at 8 weeks)
 - Mean difference of mental QOL from end of treatment compared to baseline.
 - Rank-sum test or paired t test depending on data distribution to compare mental QOL from end of treatment compared to baseline
 - Mean difference of mental QOL at end of follow-up without treatment compared to baseline
 - Rank-sum test or paired t test depending on data distribution to compare mental QOL from end of follow-up without treatment compared to baseline
 - Mean difference of mental QOL at end of follow-up without treatment compared to mental QOL at end of treatment

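### Opioid dose is defined among current users at each visit, but is compared between visits with no rule for which patients enter or what value a non-user takes

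*Combined protocol and SAP*

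**What the plan says.** Section 3, Exploratory outcomes, item 5 is the "Mean reported daily opioid dose for patients using prescription opioids at time of assessment", measured at baseline, 4 weeks and 8 weeks. Item 4 is its companion: "Opioid use (yes/no binary answer) at each assessment", at the same three times.

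In Section 5, the MME block under Exploratory endpoints lists a mean and SD at each of the three times, three mean differences and three tests. Examples are "Mean difference of MME at end of follow-up without treatment compared to baseline" and "Rank-sum test or paired t test depending on data distribution to compare MME from end of treatment compared to baseline". The block's heading and entries do not mention current users, give no denominator, and assign no dose to a patient who is not taking opioids.

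Other relevant statements:
- Section 5, Statistical analysis: "All analyses will be performed according to the intention-to-treat principle".
- Section 5, end of the analysis list: missing data are handled by multiple imputation.
- Section 3, Home-based treatment period: pain medication may be started or continued during the study.
- Section 5, opioid-use block: McNemar tests compare the proportion of users between visits.
- Exclusion criterion 8 removes longer-term daily users, beginning "Self-reported daily use of opioids for > 12 months for weak opioids", so a mix of users and non-users is possible at baseline.

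**The concern.** Being a user at an assessment is a status observed after treatment starts, and the plan expects that it may change: it re-asks the question at each visit and tests for a change in the proportion. A mean restricted to current users is a fair description of one visit. Subtracting two such means is different, because the second may cover different patients from the first. Someone who stops leaves the later mean, and someone who starts joins it. The rank-sum option, as named, is an unpaired test and would permit the same comparison across different patients.

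The paired options do not settle the matter. A paired comparison needs a dose at both visits. Without a value for non-users, only users at both visits qualify, so everyone who stopped or started is left out.

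At stake is a descriptive result in pilot data meant to inform a larger trial. Section 1 presents the treatment as a possible route to opioid-free pain therapy, and stopping opioids is the result that a users-only dose line can show as a rise.

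**Working it through.** **Inputs.** From the documents: 10 treated patients (Section 5, Sample size calculation). The documents give no opioid-use rate and no dose, so every dose below is assumed. There is no figure in the plan to reproduce.

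**General rule.** Let m of the 10 patients use opioids, with mean dose M among users, and let all other doses stay unchanged.

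- One user on dose d stops. The new users-only mean is (mM − d)/(m − 1), a change of (M − d)/(m − 1). The all-10 mean, with non-users at 0, changes by −d/10. The signs differ whenever d < M.
- One non-user starts on dose s. The new users-only mean is (mM + s)/(m + 1), a change of (s − M)/(m + 1). The all-10 mean changes by +s/10. The signs differ whenever s < M.

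**Worked case, 4 users on 10, 10, 40 and 60.** M = 120/4 = 30; all-10 mean = 120/10 = 12.

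- One 10 stops: users-only 110/3 = 36.7; all-10 110/10 = 11.
- Both 10s stop: users-only 100/2 = 50; all-10 100/10 = 10.
- The 60 stops: users-only 60/3 = 20; all-10 60/10 = 6 (same direction).
- A non-user starts on 10: users-only 130/5 = 26; all-10 130/10 = 13.
- A non-user starts on 60: users-only 180/5 = 36; all-10 180/10 = 18 (same direction).

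**Range over other assumed doses, one stopper.** Where two results are given, the first is the lowest-dose user stopping and the second the highest-dose user stopping.

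| Users and doses | Users-only mean | All-10 mean |
|---|---|---|
| 1 user: 30 | 30 to undefined | 3 to 0 |
| 2 users: 10, 60 | 35 to 60, or 35 to 10 | 7 to 6, or 7 to 1 |
| 4 users: 25, 28, 32, 35 | 30 to 31.7, or 30 to 28.3 | 12 to 9.5, or 12 to 8.5 |
| 4 users: all 30 | 30 to 30 | 12 to 9 |
| 6 users: 10, 10, 20, 30, 50, 60 | 30 to 34, or 30 to 24 | 18 to 17, or 18 to 12 |

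With 6 users, if both 10s stop, users-only goes from 30 to 160/4 = 40 and all-10 from 18 to 160/10 = 16.

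**Paired over users at both visits.** The remaining users keep their doses, so the change is 0 in every case that has a remaining user. There is no false rise, but the stopping or starting is invisible.

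**No change of status.** Both means change by the same total divided by m or by 10, so the signs agree.

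**The case against.** The strongest reply has three parts.

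First, the set is named. Outcome 5 says current users, and Section 5 uses short headings for outcomes already defined in Section 3, so the ordinary reading is that the definition carries through. This stands. A reader might infer that the analysis set is wholly unspecified, and the text does not support that. The definition does not, however, say who enters a between-visit difference or test.

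Second, outcome 4 is reported at the same visits. With complete data, the proportion of users times the users-only mean gives the all-patient mean: 0.4 × 30 = 12 before and 0.2 × 50 = 10 after. A reader who sees both lines can recover the direction of total consumption. This also stands, with limits. Missing visits break the identity (the plan expects about 10% attrition), and within-patient differences, their spread and the tests cannot be recovered.

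Third, dose among users beside the proportion of users is a legitimate two-part description, and the rank-sum wording runs through all the continuous before-after endpoints. Both are true. They argue for keeping the users-only mean, but they do not supply a rule for the MME comparisons.

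Two further inferences go beyond the documents. One is that the intention-to-treat sentence contradicts outcome 5: it is a single general statement in a one-arm study and need not conflict with an outcome defined in users. The other is that non-users would be given imputed doses: a recorded no is observed data, and nothing says that it would be treated as missing.

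**Conclusion.** The point holds as a minor one. The outcome definition names current users, but the planned between-visit comparisons do not say which patients enter or what a non-user contributes. Carried through as written, the definition allows a between-visit dose change that reflects who is in the mean and can have the opposite sign to the change in total consumption.

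The size in this trial cannot be known. A reversal needs a user below the mean dose to stop, or a non-user to start below it, with other changes not outweighing this; the illustrations hold other doses fixed. They show that a reversal is possible, not that it will occur, and several of them show none.

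The consequence is limited. The outcome is exploratory, no primary outcome uses MME, there are 10 patients, and the plan itself says "The study will be under powered to address any clinical outcomes".

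**What to change.** For the three between-visit MME comparisons in Section 5:

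- Use participants who started the intervention and have opioid data at both visits being compared.
- Score a confirmed no to prescription opioid use as 0 mg. A skipped answer stays missing; Section 6 lets participants skip questions, so the distinction matters.
- Use a paired t or signed-rank test in place of rank-sum.
- Keep the users-only mean of outcome 5 as a descriptive line, with its n at each visit, beside the outcome 4 proportions.

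No new data are needed, since the yes/no item is already collected at baseline, week 4 and week 8. The cost is a small change to the analysis definition, to be communicated to the IRB as Section 7 requires for amendments.

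The downside is a distribution with many zeros. With k non-zero differences, the smallest two-sided exact signed-rank p is 2 × 0.5^k: 0.125 for k = 4, 0.0625 for k = 5 and 0.031 for k = 6. Two-sided testing is assumed here, as the plan does not state sidedness. With five or fewer patients changing dose, the test cannot reach the plan's 0.05 threshold, so the comparison should be read descriptively.
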